# Management of Anemia including Evaluation for MDS/AML and Follow-up of Patients who Discontinue Treatment with Ongoing Anemia:

- If the patient develops anemia CTCAE Grade ≥ 3, rucaparib treatment should be held until the anemia improves to CTCAE Grade ≤ 2 whereupon daily dosing may then be resumed at either the same dose or a lower dose, per investigator discretion.
- If the duration of dosing is interrupted for > 21 consecutive days due to anemia CTCAE Grade ≥ 3, treatment should be permanently discontinued, unless otherwise agreed and documented between the investigator and the sponsor or designee.

- In addition, if anemia CTCAE Grade ≥ 3 persists for > 14 consecutive days, or a
  dependence upon blood transfusion occurs, then weekly complete blood counts
  should be performed until resolution of the event.
- If, after 42 days of interruption of rucaparib, the anemia has not improved to CTCAE Grade ≤ 1 then the patient should be referred to a hematologist and analysis of the bone marrow with cytogenetic studies are recommended according to standard hematologic practice.
- The bone marrow analysis may include a bone marrow aspirate (for cellular morphology, cytogenetic analysis, and flow cytometry) and a core biopsy (for bone marrow cellularity).

# Management of Rucaparib Treatment-Emergent ALT/AST Elevations:

- Grade 4 ALT/AST elevations: hold rucaparib until values have improved to Grade 2 or better, then resume rucaparib with a dose reduction. If toxicity is ascribed to nivolumab alone then you may resume without a dose reduction. Monitor liver function tests weekly for 3 weeks after rucaparib has been restarted.
- Grade 3 ALT/AST elevations, in the absence of other signs of liver dysfunction, should be managed as follows:
  - o Monitor liver function tests weekly until improvement to ≤ Grade 2.
  - Continuation of rucaparib with elevation of ALT/AST up to Grade 3 is permitted provided bilirubin is < ULN.

  - If patient has Grade 3 ALT/AST elevation and continues on rucaparib, and levels do not decline within 2 weeks or they continue to rise, treatment interruption and resolution to ≤ Grade 2 will be required before rucaparib can be resumed, either at the current dose or at a reduced dose.

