# **Rucaparib Dose Modification Criteria**

Treatment with rucaparib should be held if any of the following are observed and a dose reduction should be considered or implemented.

- Grade 3 or 4 hematologic toxicity. Anemia should be managed as described below
- Grade 3 or 4 non-hematologic toxicity (except for alopecia, nausea, vomiting, or diarrhea adequately controlled with systemic antiemetic/antidiarrheal medication administered in standard doses according to the study center routines). Grade 3 or Grade 4 ALT/AST elevations should be managed as described below
- In addition, and at the discretion of the investigator, the dose of rucaparib may be held and/or reduced for unremitting Grade 2 toxicity not adequately controlled by concomitant medications and/or supportive care.
- For patients who meet treatment interruption guidelines above, treatment with rucaparib should be held until the toxicity improves to ≤ CTCAE Grade 2. Twice daily dosing may then be **resumed at either the same dose or a lower dose, per investigator discretion**. If treatment is resumed at the same dose, and the patient experiences the same toxicity, treatment should be interrupted, then resumed at a reduced dose following resolution of the event to ≤ CTCAE Grade 2. If the patient continues to experience toxicity, additional dose reduction steps are permitted; however, the investigator should consult with the sponsor's medical monitor before reducing to 300 mg BID. If a patient continues to experience toxicity despite dose reduction steps to 300 mg BID, or if dosing with rucaparib is interrupted for > 21 consecutive days due to toxicity, treatment should be discontinued, unless otherwise agreed and documented between the investigator and the sponsor.

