#### Rucaparib Re-treatment Criteria

Treatment may resume if:

- ANC  $\geq 1.0 \times 10^9/L$
- Platelet count ≥ 75 x 10^9/L
- Non-hematologic toxicities have returned to baseline or ≤ CTCAE Grade 1 severity (or, at the investigator's discretion, ≤ CTCAE Grade 2 severity if not considered a safety risk for the patient). Grade 3 or Grade 4 ALT/AST elevations should be managed as described above.

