# 8.2.3 Potential Drug Induced Liver Injury (DILI)

Wherever possible, timely confirmation of initial liver-related laboratory abnormalities should occur prior to the reporting of a potential DILI event. All occurrences of potential DILIs, meeting the defined criteria, must be reported as SAEs.

Potential drug induced liver injury is defined as:

- AT (ALT or AST) elevation > 3 times upper limit of normal (ULN) AND
- Total bilirubin > 2 times ULN, without initial findings of cholestasis (elevated serum alkaline phosphatase)
   AND
- 3) No other immediately apparent possible causes of AT elevation and hyperbilirubinemia, including, but not limited to, viral hepatitis, pre-existing chronic or acute liver disease, or the administration of other drug(s) known to be hepatotoxic.

While treatment is interrupted, the patient should be evaluated for the presence of confounding factors including malignant disease in the liver, co-administration of other suspect drugs, cholestasis, and viral or autoimmune hepatitis that could have caused the laboratory abnormalities. Other laboratory investigations of liver function such as international normalized ratio (INR) should be implemented as indicated. If no alternative cause is identified, rucaparib must be permanently discontinued.

All cases of possible DILI should be followed until all abnormalities have returned to normal, returned to baseline levels, or an alternative cause is found to explain the combination of the increased transaminases and total bilirubin.

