# 8.4 Serious Adverse Event Reporting Guidelines

# 8.4.1 Reporting procedures for multi-site trials

All serious adverse events (SAEs) and unanticipated problems (UPs), regardless of causality to study drug, will be reported to the Principal Investigator and also to the Coordinating Center. All SAEs and UPs must be reported to the Coordinating Center within 24 hours of first awareness of the event. Events should be reported using the Coordinating Center's SAE form as available in the study database. A copy of the SAE form as available in the study database should be sent to the Coordinating Center via fax at [contact] or via email to [contact] within 24 hours of the site's knowledge of the event.

Follow-up information must also be reported within 24 hours of receipt of the information by the investigator.

All SAEs and UPs will be reported to the IRB per current institutional standards.

The Coordinating Center will disseminate information regarding SAEs and UPs to the participating sites within 5 days of review of the information by the Coordinating Center's Principal Investigator (or designee in the event of extended absence) only in the case that the event(s) is believed to be related (i.e., possibly, probably, or definitely) to the study drug. The Coordinating Center will be responsible for reporting of events to the FDA and supporters, as appropriate (outlined below).

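### The Grade 4 ALT/AST rule in Section 5.2 orders rucaparib to be resumed in a case where Section 8.2.3 requires it to be stopped for good

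*Combined protocol and SAP*

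**What the plan says.** Section 5.2, under the heading on treatment-emergent ALT/AST elevations, gives this rule for Grade 4: "Grade 4 ALT/AST elevations: hold rucaparib until values have improved to Grade 2 or better, then resume rucaparib with a dose reduction". Its one qualifier concerns attribution: "If toxicity is ascribed to nivolumab alone then you may resume without a dose reduction". That relaxes the dose reduction and does not bar a restart.

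The neighbouring Grade 3 rule is more guarded. It applies only when there are no other signs of liver dysfunction, and it adds: "Continuation of rucaparib with elevation of ALT/AST up to Grade 3 is permitted provided bilirubin is < ULN". The re-treatment criteria, also in 5.2, set recovery limits for non-hematologic toxicities in general but then say: "Grade 3 or Grade 4 ALT/AST elevations should be managed as described above".

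Section 8.2.3 defines potential DILI by three criteria that must all be met: ALT or AST above 3 x ULN; "Total bilirubin > 2 times ULN, without initial findings of cholestasis"; and no other immediately apparent cause. It calls for a work-up while treatment is interrupted and then states: "If no alternative cause is identified, rucaparib must be permanently discontinued".

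Section 5.2 does not mention DILI or Section 8.2.3. Section 5.3 mentions potential DILI only as something to report as an SAE, and points to Appendix III.

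**The concern.** Dose decisions are made from Section 5.2, while the mandatory stop sits among the adverse event definitions in Section 8. A site that follows the Grade 4 rule as printed would restart rucaparib in a patient whom the protocol's own safety rule says must never receive it again.

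The safeguards also run the wrong way round. The milder Grade 3 rule carries a bilirubin condition for continuing, but the Grade 4 rule carries none for resuming.

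What is at stake is re-exposure after unexplained liver injury. No endpoint, sample size or analysis is affected. The population makes the question a practical one: Section 9.1.9 lists ALT and AST increases among the most common laboratory abnormalities with rucaparib, and Section 3.1 admits patients with Child-Pugh B7, and with ALT/AST up to 5 x ULN if they have liver metastases.

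**Working it through.** The protocol states no figure on this point to reproduce. The check is a comparison of rules, followed by an illustrative calculation.

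**Step 1: line up the rules.** Three facts decide which instruction applies: the ALT/AST grade (3 or 4), whether the bilirubin criterion of 8.2.3 is met, and whether work-up finds an alternative cause. That gives 2 x 2 x 2 = 8 cases. The documents do not print the CTCAE cut-offs, so I assume that Grade 3 and Grade 4 both lie above 3 x ULN.

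| ALT/AST | Bilirubin criterion | Other cause | Section 5.2 | Section 8.2.3 | Result |
|---|---|---|---|---|---|
| Grade 4 | met | none | directs restart after recovery | mandatory stop | contradiction |
| Grade 4 | met | found | directs restart after recovery | no stop required | no conflict |
| Grade 4 | not met | either (2 cases) | directs restart after recovery | not triggered | no conflict |
| Grade 3 | met | none | permits restart | mandatory stop | permission against a must |
| Grade 3 | met | found | permits restart | no stop required | no conflict |
| Grade 3 | not met | either (2 cases) | continuation or restart rules | not triggered | no conflict |

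The total is 1 direct contradiction, 1 permission set against a must, and 6 with no conflict. These are counts of rule combinations, not frequencies. In the Grade 3 row with the bilirubin criterion met and no cause found, the specific Grade 3 rule drops out because other liver dysfunction is present. The general dose modification rule then applies, and it allows resumption without ordering it.

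**Step 2: look for an exception elsewhere in 5.2.**
- The attribution sentence covers toxicity ascribed to nivolumab alone. That is an identified cause, so it lies outside the contradictory case.
- The re-treatment criteria treat raised bilirubin as a separate non-hematologic toxicity, which has to recover. That can delay a restart but does not forbid one, whereas 8.2.3 forbids it whether or not values recover.
- The general dose modification rule says "the investigator should consult with the sponsor's medical monitor before reducing to 300 mg BID", and requires sponsor agreement to continue after an interruption of more than 21 days. It sets no consultation requirement for an earlier first restart at a higher dose.

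**Step 3: a worked case.** A patient on 600 mg BID has Grade 4 ALT, bilirubin 2.5 x ULN and normal alkaline phosphatase, and no cause is found. By day 14 ALT is back to Grade 2 and bilirubin has settled within the re-treatment limits.
- Section 5.2 with Table 2: restart one dose level down, at 500 mg BID. Day 14 is within 21 days and 500 mg is above 300 mg, so neither sponsor-contact trigger in the dose modification rule applies.
- Section 8.2.3: never restart.

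**Step 4: how often could it arise?** The documents give no frequency. With an assumed per-patient risk p and n = 32 (Section 11.2), P(at least one) = 1 - (1 - p)^32:
- p = 0.5%: 1 - 0.995^32 = 14.8%
- p = 1%: 1 - 0.99^32 = 27.5%
- p = 3%: 1 - 0.97^32 = 62.3%

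This is the chance that a qualifying patient occurs, not the chance that one is wrongly re-exposed.

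**The case against.** The best counter-argument is that the two sections can be read in sequence. Section 8.2.3 describes a narrower syndrome and presupposes that treatment is already interrupted, so a site could hold under 5.2, work up under 8.2.3, and stop if no cause emerges. A specific mandatory rule would ordinarily override a general one. That is a sensible reading and many investigators would adopt it, but no text states that precedence, and the Grade 4 rule is worded as an instruction.

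Other safeguards exist. Unacceptable adverse events (5.6) and the physician's judgment of the patient's best interest (5.9.4) allow rucaparib to be stopped, but both are discretionary where 8.2.3 is not. Potential DILI must be reported as an SAE, and Section 8.4.1 says: "All SAEs and UPs must be reported to the Coordinating Center within 24 hours of first awareness of the event". The Principal Investigator is also told, and follow-up information is due within 24 hours. Central oversight would probably be engaged before ALT falls to Grade 2, which lowers the risk. Still, no text makes the restart wait for the work-up.

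It can also be said that few patients would qualify. The third criterion in 8.2.3 excludes cases with another known hepatotoxic drug, and every patient starts on nivolumab. If nivolumab counts as such a drug, the definition is rarely met. The protocol does not settle this, so the size of the affected group is uncertain. The group is still not empty: 5.2 allows rucaparib to continue alone after nivolumab is stopped.

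Finally, the hepatic algorithm figure in Appendix III is not available in the text reviewed, so nothing here rests on its content. The readable part of that appendix concerns immuno-oncology agents.

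**Conclusion.** The concern holds. For a patient with Grade 4 ALT/AST, bilirubin above 2 x ULN without initial cholestasis and no cause found, Section 5.2 directs a restart and Section 8.2.3 requires a permanent stop. Smaller bilirubin rises, cholestatic pictures and cases with an identified cause, including toxicity ascribed to nivolumab alone, are not affected. At Grade 3 the mismatch is weaker, because 5.2 permits resumption without ordering it.

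The conclusion rests on the wording of the two sections and on the assumption that Grade 4 ALT/AST exceeds 3 x ULN. It does not depend on the illustrative risks. The conflict should be fixed because the consequence for an affected patient could be serious and the remedy is small.

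**What to change.** Add an exception at the head of the ALT/AST rules in Section 5.2, along these lines:

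> If the potential DILI criteria in Section 8.2.3 are met at any ALT/AST grade, interrupt rucaparib and carry out the 8.2.3 evaluation. If that evaluation finds no alternative cause, do not restart rucaparib. Section 8.2.3 takes precedence over the resumption rules in this section.

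Two optional clarifications would help. Section 8.2.3 could state that study nivolumab alone does not count as another hepatotoxic drug when deciding whether the definition is met. Section 5.3 could cite 8.2.3 alongside Appendix III.

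The cost is a short protocol amendment and a memo to sites. No tests, visits or patients are added.

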#### Management of Creatinine Elevation:

- Rucaparib can cause creatinine elevation of any grade in 92% of the patients
   (1% grade 3-4) possibly due to potent inhibition of the MATE1, MATE2-K and
   OCT1 transporters. The majority of reported grade 1-2 creatinine elevations
   stabilize with continued rucaparib treatment without dose modification. However,
   grade 2 elevation of creatinine can also be due to autoimmune nephritis from
   nivolumab. To help identify whether rucaparib or nivolumab is the underlying
   etiology for the creatinine elevation all subjects will undergo repeat CMP on cycle
   1 day 8.
  - Grade 2 creatinine elevation on cycle 1 day 8: Hold rucaparib and recheck on cycle 1 day 15. If creatinine is improved to grade 1 (≤1.5 x ULN) on day 15, then resume rucaparib at full dose.
  - Grade 3-4 creatinine elevation: Hold rucaparib and consider a dose reduction.

#### Rucaparib Re-treatment Criteria

Treatment may resume if:

- ANC  $\geq 1.0 \times 10^9/L$
- Platelet count ≥ 75 x 10^9/L
- Non-hematologic toxicities have returned to baseline or ≤ CTCAE Grade 1 severity (or, at the investigator's discretion, ≤ CTCAE Grade 2 severity if not considered a safety risk for the patient). Grade 3 or Grade 4 ALT/AST elevations should be managed as described above.

# 5.3 Management Algorithms for Immuno-Oncology Agents

Nivolumab is associated with immune related adverse events secondary to the unrestrained T cell activation. Management algorithms have been developed to assist investigators in assessing and managing the following groups of adverse events:

Gastrointestinal

Renal

Pulmonary

Hepatic

Endocrinopathies

Skin

Neurological

Wherever possible, timely confirmation of initial liver-related laboratory abnormalities should occur prior to the reporting of a potential drug-induced liver injury (DILI) event. All occurrences of potential DILIs, meeting the defined criteria in Appendix III must be reported as SAEs.

Please refer to Appendix III for algorithm details.

#### 5.4 Concomitant Medications/Treatments

The following concomitant medications or treatments are not permitted while the patient is currently receiving therapy on the protocol:

- Other investigational agents
- Concurrent radiation

# Effect of Other Drugs on Rucaparib

Rucaparib is primarily metabolized by CYP2D6 and to a lesser extent by CYP1A2 and CYP3A4. Caution should be used for concomitant use of strong CYP3A4 inhibitors or inducers.

#### Effect of Rucaparib on Other Drugs

Rucaparib reversibly inhibits CYP1A2, CYP2C19, CYP2C9 and CYP3A, and to a lesser extent CYP2C8, CYP2D6, and UGT1A1. It is also a potent inhibitor of MATE1 and MATE2-K, and a moderate inhibitor of OCT1. Caution should be used for concomitant use of CYP substrates with narrow therapeutic index as listed below.

| CYP Enzyme | ne Substrates with Narrow Therapeutic Index                                                                                                          |  |  |  |  |  |
|------------|------------------------------------------------------------------------------------------------------------------------------------------------------|--|--|--|--|--|
| CYP1A2     | Tizanidine, theophylline                                                                                                                             |  |  |  |  |  |
| CYP2C9     | Warfarin, phenytoin                                                                                                                                  |  |  |  |  |  |
| СҮРЗА      | Alfentanil, astemizole, cisapride, cyclosporine, dihydroergotamine, ergotamine, fentanyl, pimozide, quinidine, sirolimus, tacrolimus and terfenadine |  |  |  |  |  |

# 5.5 Other Modalities or Procedures

None

#### 5.6 Duration of Therapy

In the absence of treatment delays due to adverse events, treatment may continue for 2 years until one of the following criteria apply:

- Disease progression as defined in Section 7.0
- Inter-current illness that prevents further administration of treatment
- Unacceptable adverse event(s)

- Patient voluntarily withdraws from treatment OR
- General or specific changes in the patient's condition render the patient unacceptable for further treatment in the judgment of the investigator

#### 5.7 Off Treatment Criteria

Patients will be removed from protocol therapy when any of the criteria listed in Section 5.6 apply. Document in the source the reason for ending protocol therapy and the date the patient was removed from treatment. All patients who discontinue treatment should comply with protocol specific follow-up procedures as outlined in Section 5.8. The only exception to this requirement is when a subject withdraws consent for all study procedures or loses the ability to consent freely.

# 5.8 Duration of Follow-Up

After treatment discontinuation, follow-up for survival and initiation of any other anticancer therapies will be documented every 3 months via telephone or office visit documentation for up to 2 years from treatment discontinuation or until death, whichever comes first, or 3 years after first date of treatment initiation for those that remain on treatment. Patients removed from treatment for unacceptable adverse events will be followed until resolution or stabilization of the adverse event.

# 5.9 Off Study Criteria

Patients can be taken off study treatment at any time at their own request, or they may be withdrawn at the discretion of the investigator for safety, behavioral or administrative reasons. The reason(s) for discontinuation from study treatment/study participation will be documented and may include:

- **5.9.1** Patient withdraws consent (termination of treatment and follow-up);
- **5.9.2** Loss of ability to freely provide consent through imprisonment or involuntary incarceration for treatment;
- **5.9.3** Patient is unable to comply with protocol requirements;
- **5.9.4** Treating physician judges continuation on the study would not be in the patients best interest;
- **5.9.5** Patient becomes pregnant (pregnancy to be reported along same timelines as a serious adverse event);
- **5.9.6** Development of second malignancy (except for basal cell carcinoma or squamous cell carcinoma of the skin) that requires treatment, which would interfere with this study;
- 5.9.7 Lost to Follow-up. If a research subject cannot be located to document survival after a period of 2 years, the subject may be considered "lost to follow-up." All attempts to contact the subject during the two years must be documented;
- **5.9.8** Termination of the study by the Sponsor, the University of Michigan or the FDA;
- **5.9.9** Patient completes protocol treatment and follow-up criteria;
- **5.9.10** Treatment delay of more than 28 days from last intended therapy;

**5.9.11** Patient has confirmed progressive disease as per RECISTv1.1/irRECIST criteria and/or, at the discretion of the treating physician, exhibits clinical progression which warrants removal from the study.

# 5.10 Patient Replacement

All patients that receive at least one dose of study therapy will be considered evaluable for toxicity and will be considered a member of the intent-to-treat (IIT) population.

Patients enrolled on the study will be replaced and not considered a member of the IIT for the following reasons

- 1. Patients who did not receive even one dose of investigational therapy on study.
- 2. Patients that withdraw consent for study therapy prior to first response evaluation not secondary to toxicity.
- 3. Patients meeting off study criteria 5.9.1 and/or 5.9.3 not secondary to toxicity.
- 4. Patients meeting off study criteria 5.9.2 and/or 5.9.5

We expect the proportion of patients needed to be replaced to be extremely small for this clinical trial, at or less than 10% of those enrolled. Maximum enrollment to this trial will be increased to 35 patients if the necessity to replace patients is encountered.

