# 2.4 Endpoints Assessment

- 2.4.1 Primary Endpoint Assessment: For the intent-to-treat population the progression-free survival (PFS) rate will be defined as the proportion of patients alive and without radiological or clinical progression (leading to withdrawal from the study) at 4 months and patient replacement as specified in section 5.10.
- 2.4.2 Secondary Endpoint Assessment: Overall response rate (ORR) will be determined as per the combined RECISTv1.1 and irRECIST criteria. The progression-free survival (PFS) will be defined as time from date of treatment to date of radiological or clinical progression (leading to withdrawal from the study), or death from any cause, whichever comes first. PFS1 will be from start of study treatment and will be the primary study endpoint. PFS2 will be from start of 1st line platinum therapy. Overall survival (OS) will be defined from the date of treatment to either date of death or censoring. OS1 will be from start of study treatment. OS2 will be from start of 1st line platinum therapy. Follow-up time will be censored at the date of last disease evaluation. Adverse events and reportable serious events are defined by the study protocol (NCI Common Toxicity Criteria for Adverse Events (CTCAE) v5.0).

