#### 7.1.1 Definitions

Evaluable for toxicity. All patients will be evaluable for toxicity from the time of their first treatment with study drug.

Evaluable for primary endpoint, PFS at 4 months. All patients that receive at least one dose of study therapy will be considered evaluable. Patients enrolled and/or randomized to therapy but that never receive study therapy will be replaced.

Evaluable for objective response. All enrolled patients who have measurable disease at registration, receive at least 1 cycle(s) of therapy, and have their disease re-evaluated will be considered evaluable for response. These patients will have their response classified according to the definitions stated below. (Note: Patients who exhibit objective disease progression prior to the end of cycle 1 will be considered progressive disease.)

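### Section 5.10 labels as intent-to-treat a primary set that removes and replaces dosed patients for post-dose events, and other sections define the set differently

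*Combined protocol and SAP*

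**What the plan says.** Section 5.10 opens by saying that patients with at least one dose "will be considered evaluable for toxicity and will be considered a member of the intent-to-treat (IIT) population". It then lists four reasons for which an enrolled patient is replaced and is not a member of that population:

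1. never dosed;
2. withdrawal of consent to study therapy before the first response evaluation, unless due to toxicity;
3. "Patients meeting off study criteria 5.9.1 and/or 5.9.3 not secondary to toxicity", that is, withdrawal of consent to treatment and follow-up (5.9.1) or "Patient is unable to comply with protocol requirements" (5.9.3);
4. incarceration (5.9.2) or pregnancy (5.9.5).

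Item 2 has a time limit. Items 3 and 4 have none. On numbers, 5.10 expects at most 10% of those enrolled to be replaced and adds: "Maximum enrollment to this trial will be increased to 35 patients if the necessity to replace patients is encountered".

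Two sections make 5.10 the governing rule. Section 2.4.1 defines the primary endpoint for the intent-to-treat population "at 4 months and patient replacement as specified in section 5.10". Section 11.3 makes the 5.10 population the set for the primary, secondary and safety endpoints.

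Other sections differ:

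- 7.1.1, for 4-month PFS: "All patients that receive at least one dose of study therapy will be considered evaluable" and "Patients enrolled and/or randomized to therapy but that never receive study therapy will be replaced".
- 11.2 counts only patients who comply with treatment and are observed for PFS. It replaces those who do not comply or are lost, unless toxicity is the cause.
- The synopsis (Statistical Methodology) says the same without the toxicity exemption.
- 11.4 uses a Kaplan-Meier estimate when loss or early discontinuation occurs.
- 5.2, 7.1.1 and 7.2 assess toxicity or safety in all dosed patients.

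**The concern.** Only the never-dosed reason fits the opening sentence of 5.10. The other three can arise after dosing, and a set that drops dosed patients for post-dose events is not intent-to-treat. Because items 3 and 4 have no time limit, a literal reading removes a patient known to be progression-free at month 4 who becomes unable to comply at month 6. It also removes a patient who progressed at month 3 and later withdraws consent to follow-up. In both cases the primary outcome is already known.

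The trial is single-arm and open-label with 32 patients, so two or three patients decide a borderline result, and whoever classifies a departure may know the outcome. For safety, the 11.3 rule would leave out patients who were exposed to the combination.

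**Working it through.** **Inputs.** From 11.2: null rate 0.63, target 0.85, n = 32, one-sided 5% test, power 80%. From 5.10: maximum enrolment 35, so at most 35 − 32 = 3 replacements if 32 are kept. The documents give no cutoff and no removal rates. The cutoff below is derived, and the removal rates are assumptions.

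**The plan's own figure.** With X ~ Bin(n, p), take the smallest r for which P(X ≥ r | 32, 0.63) ≤ 0.05.

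- r = 25: 0.0523, too large.
- r = 26: 0.0215, accepted. Power P(X ≥ 26 | 32, 0.85) = 0.805.

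This reproduces the stated 80%. No stated figure is disputed. The question is which patients make up the 32.

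**Effect on a borderline result.** Suppose 35 are dosed, three are removed, and their 4-month status is known. The p-value is P(X ≥ x | n, 0.63).

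| Result after removal | Removed patients progression-free | Result in all dosed |
|---|---|---|
| 26/32, p = 0.022 | 0 of 3 | 26/35, p = 0.112 |
| 26/32, p = 0.022 | 1 of 3 | 27/35, p = 0.056 |
| 26/32, p = 0.022 | 2 of 3 | 28/35, p = 0.025 |
| 26/32, p = 0.022 | 3 of 3 | 29/35, p = 0.009 |
| 25/32, p = 0.052 | 3 of 3 | 28/35, p = 0.025 |

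In the first four rows the conclusion reverses only if at least two of the three failed. The last row goes the other way: removal turns a positive result into a negative one.

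**Type I error of the 26/32 rule.** Simulation with true 4-month PFS 0.63, and at most three patients removed and replaced:

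| Failures removed | Successes removed | Type I error | Mean share of dosed patients removed |
|---|---|---|---|
| 0% | 0% | 2.2% | 0% |
| 10% | 10% | 2.2% | – |
| 10% | 0% | 3.9% | 3.5% |
| 20% | 0% | 6.2% | 6.1% |
| 30% | 0% | 8.3% | 7.5% |
| 20% | 5% | 4.4% | – |
| 0% | 10% | 1.2% | – |

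No run can exceed 3/35 = 8.6% removed, so every row lies within the 10% that 5.10 expects.

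**When 4-month status is unknown.** If three of 35 are censored before any event, they leave the risk set before the Kaplan-Meier curve first drops. The estimate is then that of the other 32, for example 26/32 = 81.3%. Keeping these patients as censored gives the same estimate as removing them.

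**The case against.** The strongest reply is that the plan does name a governing rule. Sections 2.4.1 and 11.3 both point to 5.10, the synopsis speaks of 32 patients meeting intent-to-treat guidelines with up to 35 enrolled, and the 5.10 list can be read as exceptions to its opening sentence. On that view the faults are a wrong label and unharmonised text, and a time limit on item 3 would remove the odd cases. The replacement rule is also prespecified and expected to be used rarely. Much of this stands, and it is why the point is not graded higher. It does not make the 5.10 set intent-to-treat, restore known outcomes that a literal reading discards, or justify leaving dosed patients out of safety.

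A reader might infer more than the documents support:

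- *That the rule favours the treatment.* PFS is the "time from date of treatment to date of radiological or clinical progression (leading to withdrawal from the study), or death from any cause", so clinical progression that leads to withdrawal is already an event. Removal on the physician's judgment (5.9.4) is not a replacement reason, and items 2 and 3 exempt toxicity. Removal can discard successes as well as failures.
- *That the analyst may freely choose among the definitions.* The pointers to 5.10 argue against this.
- *That 11.4 flatly contradicts replacement.* Its Kaplan-Meier rule is conditional and may be a fallback for patients who are not replaced, for example once enrolment reaches 35.
- *That the absence of 5.9.7 from the 5.10 list shows a conflict over loss to follow-up.* 5.9.7 concerns survival that cannot be documented over 2 years, which is not the same as loss before the 4-month assessment.
- *That exclusions could continue past three.* That would leave fewer than the 32 evaluable patients the plan commits to accrue.

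**Conclusion.** The point holds and should be fixed. The primary set is a modified intent-to-treat set labelled intent-to-treat. 7.1.1, 11.2 and the synopsis do not agree with it or with one another, and 11.3 carries the reduced set into safety against 5.2, 7.1.1, 7.2 and the opening sentence of 5.10.

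The effect on the primary result is possible but unquantified, in either direction. With at most three removals, type I error stays at 2.2% if removal is unrelated to outcome. It passes 5% in the illustrations only when removal falls heavily on failures: 6.2% at 20% and 8.3% at 30% of failures with no successes removed, but 4.4% at 20% of failures with 5% of successes. These rates are assumed, and the 26/32 cutoff is inferred from the stated power. The practical gain is confined to leavers whose 4-month status is known and to safety reporting.

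**What to change.** - Define one set, all patients with at least one dose, for the primary, secondary and safety analyses. Response may keep its measurable-disease condition.
- Replace only never-dosed patients. Delete items 2–4 of 5.10 as exclusions from analysis, and align 7.1.1, 11.2–11.4 and the synopsis.
- Count every dosed patient whose 4-month status is known, whatever the reason for leaving.
- For unknown status, keep the 11.4 Kaplan-Meier estimate with censoring at the last disease evaluation. Say plainly that this does not correct for leaving that is related to outcome.
- If a binomial test is used, set its cutoff by the number dosed: 26/32, 26/33, 27/34 or 28/35 (one-sided error 0.022, 0.041, 0.032, 0.025).

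A sensitivity analysis that counts missing status as failure is a useful option, not a correction. At 26/32, with 85% PFS in the others, its power is P(X ≥ 26 | 31, 30 or 29; 0.85) = 0.68, 0.52 or 0.35 with one, two or three leavers among 32, so it does not suit the primary analysis.

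The cost is wording, with no extra patients or visits. The reported rate may be lower. After treatment ends, 5.8 schedules follow-up only for survival and other anticancer therapy, so progression status of early leavers will often stay unknown, and this change does not alter that.
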